**Figure 1. Diagnostic Algorithm for Patients with Suspected Amyloid Cardiomyopathy (Gillmore 2016)**

Echocardiographic features suggesting/indicating cardiac amyloid include (but are not limited to) increased left ventricular wall thickness, restrictive filling pattern, abnormal left and right ventricular longitudinal strain, and atrial septal thickening.

Features suggesting/indicating cardiac amyloid on cardiac magnetic resonance imaging (CMR) include (but are not limited to) restrictive morphology, abnormal gadolinium kinetics, and extracellular volume expansion based on T1 mapping.

AApoA1 indicates apolipoprotein A-I; DPD, 3,3-diphosphono-1,2-propanodicarboxylic acid; HDMP, hydroxymethylene diphosphonate; and PYP, pyrophosphate.

Moreover, the data clearly indicate that the combined finding of grade 2 or 3 cardiac uptake on radionuclide scintigraphy and the absence of a monoclonal protein by serum immunofixation electrophoresis (IFE), urine IFE, and sFLC (Freelite) assay was 100% specific for presence of ATTR-CM (Gillmore 2016).

A diagnosis of ATTR-CM should be followed by TTR genotyping in all patients to differentiate between wild-type and variant ATTR-CM.

The main purpose of this study is to determine the prevalence of ATTR-CM among patients admitted due to LVH of unknown etiology when radionuclide bone scintigraphy or SPECT is used.

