## **8. RESEARCH QUESTION AND OBJECTIVES**

### **Primary objective**

- To assess the prevalence of patients with cardiac fixation on a radionuclide bone scintigraphy and/or Single Photon Emission Computed Tomography (SPECT) performed with 99mTc-DPD or 99mTc-PYP or 99mTc-HMDP\* among patients with (left ventricular hypertrophy) LVH from an undiagnosed etiology.

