### **9.2.2. Inclusion Criteria**

The study will enroll patients according to the eligibility criteria in participating countries. The recruiting centers will be representative of each country involved in terms of care management systems, of size and of practices (at least when performing feasibility).

To ensure equitable recruitment, each site will be limited to a 100 screened patient maximum.

All patients who met the inclusion and exclusion criteria will be invited to participate in the study.

An informed consent document, will be signed by each patient before any data collection (Appendix 1).

If a patient isn't included in the study for any reason, the non-inclusion register has to be completed (Appendix 2).

The enrollment visit will be performed at the time of inclusion, after the patients' acceptance of enrollment in the study and Informed Consent Document signature.

Data will come from medical records and will be collected in routine clinical practice. The enrollment visit will comprise a first section on patients' eligibility for every patient and a second section on the patient information, family history and clinical evaluation at the inclusion.

After the patient undergoes a Bone Scintigraphy and/or SPECT as part of standard of care (Annex 3) the images will be evaluated by the nuclear medicine specialist of the investigational center.

Scans will be defined at each site according to the internationally accepted grading:

*Grade 0 = absent cardiac uptake*

*Grade 1 = mild uptake less than bone*

*Grade 2 = moderate uptake equal to bone*

*Grade 3 = high uptake greater than bone*

For all patients with cardiac fixation at scintigraphy and/or SPECT the following data will be collected and incorporated in the CRF if available:

- Answers from questions regarding ATTR amyloidosis red flags
- Results from clinical laboratory tests and genotyping.

The patient will finish the study after this visit.

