##### **1. Inclusion Criteria.**

- a. Patient signed informed consent
- b. Males and Females
- c. Age  $\geq 50$  years
- d. Left ventricular hypertrophy (LVH) defined as end-diastolic LV maximum wall thickness (MWT)  $\geq 15$ mm in Echocardiogram.
- e. Plan to undergo or recently underwent radionuclide bone scintigraphy and/or SPECT with any of the following radio labelled tracers:  $^{99m}\text{Tc}$ -DPD or  $^{99m}\text{Tc}$ -PYP or  $^{99m}\text{Tc}$ -HMDP\*.

*\* Scintigraphy will be defined at each site according to the standard grading:*

*Grade 0 = absent cardiac uptake*

*Grade 1 = mild uptake less than bone*

*Grade 2 = moderate uptake equal to bone*

*Grade 3 = high uptake greater than bone*

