#### 9.4. Data sources

Data will be collected from medical records and routine clinical practice. As an epidemiological study, there are no specific requirements with regard to patient procedures to be performed or the treatment regimen. Data from each patient will be reported on an electronic case report form (e-CRF).

An electronic Case Report Form (e-CRF – Appendix 3) will be used for data recording. In this protocol, the term e-CRF should be understood to refer to medical records in electronic data form. The data collection method used will be an e-CRF for physicians in English.

The visit after scintigraphy/SPECT should be documented only when the bone scintigraphy is positive with tracer uptake (Grade 1, 2 or 3) or SPECT shows cardiac fixation.

It is the investigator's responsibility to ensure completion and to review and approve all e-CRFs. E-CRFs must be signed by the investigator or by an authorized staff member. These signatures serve to attest that the information contained on the e-CRFs is true. Anytime, the investigator has the final personal responsibility for the accuracy and authenticity of all clinical and laboratory data entered into the e-CRF.

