## 5 ANALYSIS SETS/POPULATIONS

### 5.1 FULL ANALYSIS SET

#### **Full Analysis Set 1 – Primary population**

Full Analysis Set 1 (FAS1) includes all patients who meet eligibility (inclusion/exclusion) criteria and with a radionuclide bone scintigraphy and/or SPECT performed with 99mTc-DPD/99mTc-PYP/99mTc-HMDP.

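### The primary result is scan positivity among LVH patients selected for scanning, but the purpose and primary objective word it as prevalence among patients with LVH of unknown etiology

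*Protocol*

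**What the plan says.** **Population claimed.** The last paragraph of protocol section 7 reads "The main purpose of this study is to determine the prevalence of ATTR-CM among patients admitted due to LVH of unknown etiology" and ends "when radionuclide bone scintigraphy or SPECT is used". The primary objective in section 8 begins "To assess the prevalence of patients with cardiac fixation on a radionuclide bone scintigraphy and/or Single Photon Emission Computed Tomography (SPECT) performed with", lists three tracers, and gives the population as patients whose LVH has no diagnosed cause. SAP sections 2 and 2.2 and the first row of the endpoint table in SAP section 8.2 use the same population. The shell of Table 15.2.1 is labelled FAS1 but describes no population.

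**Population studied.** Inclusion criterion (e) in protocol section 9.2.5 is "Plan to undergo or recently underwent radionuclide bone scintigraphy and/or SPECT with any of the following radio labelled tracers". FAS1 (SAP section 5.1) takes eligible patients "with a radionuclide bone scintigraphy and/or SPECT performed with 99mTc-DPD/99mTc-PYP/99mTc-HMDP".

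**Who orders the scan.** Not the study. Section 9.4 says "there are no specific requirements with regard to patient procedures to be performed or the treatment regimen", and section 9.1 describes every assessment as routine or guideline practice.

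**Who is scanned, according to the background.** The abstract says scintigraphy should be considered when ATTR-CM is suspected. Section 7 says when ATTR is possible, and lists age over 65, bilateral carpal tunnel syndrome, no family history of HCM, and suggestive ECG and imaging.

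**Who is removed.** The footnote to exclusion criterion (a) counts a patient as already diagnosed with TTR amyloidosis if, among other routes, cardiac fixation was seen on a bone scan.

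**Limitations and register.** Sections 9.9.1 and 9.9.2 name volunteer sites and selection of patients by investigators. Section 9.2.2 says that for patients not included "the non-inclusion register has to be completed".

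**The concern.** A prevalence needs a denominator that matches the population in its title. Here the denominator is reached only through a clinician's decision to scan, and the protocol's own account of that decision rests on features that predict the outcome. The figure is therefore a yield among scanned patients. It equals prevalence in unexplained LVH only if sites scan all such patients, or if the decision to scan is unrelated to the result. The documents state neither.

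This is the study's main result and it is meant for publication (protocol section 12). A reader of the current wording would apply it to every patient of 50 or over with unexplained wall thickness of at least 15 mm. The interval printed beside it would not warn them, because it reflects sampling error alone.

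**Working it through.** **1. The plan's own precision figure.** Inputs from protocol section 9.5: prevalence 10%, N = 1500, 95% two-sided.

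1.96 × √(0.10 × 0.90 / 1500) = 1.96 × 0.00775 = 0.0152, or 1.52 points. The stated ±1.5 is reproduced. The Wilson interval (the SAP section 8.1 method) for 150/1500 is 8.6% to 11.6%. The arithmetic is sound; what matters is what it leaves out. Section 9.5 applies the 10% to ATTR-CM, whereas the primary endpoint (SAP section 6.3) is any fixation of grade 1 to 3. The 10% below is only a convenient reference value for positivity.

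**2. Selection by referral.** Let R be the probability of being scanned for a patient who would be positive, divided by that for a patient who would be negative. The documents give no R, so every value is an assumption. With true prevalence p, yield = pR / (pR + 1 − p). At p = 10%:

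| R | Calculation | Yield |
|---|---|---|
| 0.84 | 0.084 / 0.984 | 8.5% |
| 1 | 0.100 / 1.000 | 10.0% |
| 1.17 | 0.117 / 1.017 | 11.5% |
| 1.5 | 0.150 / 1.050 | 14.3% |
| 2 | 0.200 / 1.100 | 18.2% |

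The difference reaches the whole planned precision at R of about 1.17 upward or 0.84 downward. At R = 1.5 the expected Wilson interval with N = 1500 is 12.6% to 16.1%, which excludes the true 10%.

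**3. The same effect as a mixture.** Let r be the share of eligible LVH patients who are scanned, and p0 the positivity the others would have had. Overall prevalence = r × 10% + (1 − r) × p0. With assumed r of 30–70% and p0 of 1–5%:

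- lowest: 0.3 × 10% + 0.7 × 1% = 3.7%
- highest: 0.7 × 10% + 0.3 × 5% = 8.5%

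That is 1.5 to 6.3 points below 10%. Every p0 in the range is below 10%, so this calculation can only return a lower figure; at p0 = 10% the difference is zero. It shows scale and is no evidence of direction.

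**4. Selection by exclusion.** Criterion (e) admits recently scanned patients, while the footnote to exclusion (a) removes patients already diagnosed by cardiac fixation. Let s be the share recently scanned and e the share of their positives excluded. From 10%, yield = 0.10(1 − se) / [0.10(1 − se) + 0.90]. With assumed s = 25% and e = 100%: 0.075 / 0.975 = 7.7%. With s = 50%: 0.05 / 0.95 = 5.3%.

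**5. Both together.** The effects cancel when R(1 − se) = 1. For R = 1.5 that is se = 1/3: 0.15 × 2/3 = 0.10, and 0.10 / (0.10 + 0.90) = 10%. A larger se gives a net understatement, a smaller one a net overstatement.

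**6. Whether the plan handles this elsewhere.** The remedy in section 9.9.2, trying to enroll systematically, works only among patients who already meet criterion (e). The sensitivity analyses in SAP section 8.2 compare patients before and after amendment 2. The visible text plans no count of unscanned LVH patients, no weighting and no analysis of the register.

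**The case against.** **The wording already refers to the scan.** The purpose ends "when radionuclide bone scintigraphy or SPECT is used" and the objective speaks of a scan performed with named tracers. Both phrases state how positivity is detected; neither limits the population to patients sent for a scan.

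**The denominator is disclosed.** Criterion (e), the FAS1 definition and the FAS1 label on Table 15.2.1 are all visible, and patient selection is acknowledged in general terms. This is true, and it makes the defect one of wording and interpretation rather than concealment. It leaves the objective broader than the data.

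**Referral may be broad.** Section 7 says unexplained wall thickening should prompt a search for its cause, and wall thickening is among the listed echo features suggesting amyloid. Investigators are cardiomyopathy or LVH specialists, and entry starts at age 50, so the list beginning with age over 65 is no entry rule. This objection stands against any claim about size: R could be near 1. It does not show that all such patients are scanned.

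**No interval covers selection error, and SAP section 4.1 disclaims inferential hypotheses.** Agreed; the interval is not faulty. The point is that nothing else in the plan warns of what it omits.

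**The register may not help.** It is a stand-alone document (Appendix 2 in Annex 1) whose fields are not shown, and section 9.2.2 does not say that patients with no scan planned are logged. The SAP's full table list is also separate. No remedy should depend on the register.

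**Conclusion.** The mismatch holds on the text alone: the purpose and primary objective claim prevalence in LVH of unknown etiology, while entry and FAS1 deliver positivity among LVH patients selected for scanning. Section 9.9 does not name this selection.

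A reader might infer that the published figure will be too high, perhaps by 1.5 to 6.3 points. The documents do not support that. Those figures rest on an assumed referral share and an assumed positivity in unscanned patients that was set below 10% throughout, and they treat the protocol's ATTR-CM figure as scan positivity. Referral on suspicion pushes upward; the exclusion of patients already diagnosed by fixation can push downward. The documents allow neither a net sign nor a size. They do show that a modest imbalance in scanning, R of about 1.17 or 0.84, would match the whole ±1.5 points of planned precision.

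Nor does it follow that the estimate is invalid. It is usable for patients scanned in routine care at these sites, provided the entry rules on earlier scans are settled. The claim should be narrowed to that group.

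**What to change.** 1. Restate the main purpose, primary objective, first endpoint row of SAP section 8.2 and Table 15.2.1 as prevalence *among patients with LVH of undiagnosed etiology who underwent bone scintigraphy/SPECT in routine care*. This also removes the reference to admitted patients in the purpose, which no entry criterion matches.
2. Add selection by referral for the scan to section 9.9 and to the interpretation of the result, stating that its net direction is unknown and that the interval does not cover it.
3. Reconcile inclusion criterion (e) with the footnote to exclusion criterion (a), and report how recently scanned patients with a positive result were handled.
4. If the non-inclusion register records eligible LVH patients with no scan planned, tabulate it by reason and site. Label any bounded prevalence as a sensitivity illustration with its assumptions shown.

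Cost: a narrower claim and wording changes in both protocol and SAP, with no new patients or procedures. Data collection was planned to end in June 2022 and SAP version 2 is dated July 2022, so information on unscanned patients that was not recorded may not be recoverable. Items 1 and 2 remain possible at the reporting stage.

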## **8. RESEARCH QUESTION AND OBJECTIVES**

### **Primary objective**

- To assess the prevalence of patients with cardiac fixation on a radionuclide bone scintigraphy and/or Single Photon Emission Computed Tomography (SPECT) performed with 99mTc-DPD or 99mTc-PYP or 99mTc-HMDP\* among patients with (left ventricular hypertrophy) LVH from an undiagnosed etiology.

### **Secondary objectives**

- To assess the prevalence of AL or ATTR amyloidosis in patients with cardiac fixation at the bone scintigraphy (visual grade 1 to 3) and/or SPECT;
- In patients diagnosed with ATTR Amyloidosis to assess the prevalence of hereditary (ATTRv) and wild-type (ATTRwt) ATTR amyloidosis;
- To describe TTR genetic mutations\*\* in patients with ATTRv amyloidosis;
- To assess the prevalence of patients with familial history of known cardiomyopathy (CM), polyneuropathy (PN), sudden cardiac death (SCD) among their relatives (ie, parents, siblings and 2nd /3rd degree family members).

[figure not shown]
- To assess the prevalence in patients with positive cardiac fixation at the bone scintigraphy and/or SPECT of patients with concomitant signs or symptoms of ATTR amyloidosis, ie,:
  - Sensori-motor Polyneuropathy (PN);
  - Carpal Tunnel syndrome (CTS);
  - Autonomic dysfunction;
  - Cardiological manifestations;
  - Laboratory signs;
  - Others.
- To compare the clinical and biochemical characteristics between patients with positive scintigraphy (cardiac fixation at the bone scintigraphy grade 1, 2 or 3) and/or SPECT.
- To assess the level of discrepancy in the evaluation of the scintigraphy and/or SPECT images by different evaluators

\* Bisphosphonate (99mTc-DPD/99mTc-PYP/99mTc-HMDP) Scintigraphy.

\*\* Variant and pathogenic mutation per sequencing the coding parts.

**Figure 2. Study Flow Chart**

**9. RESEARCH METHODS**

## 9.1. Study Design

TTRACK is an epidemiological multicenter and multinational study.

Patients can be enrolled from several countries listed in Appendix 5. This list is non-exhaustive and additional countries may be added to this list.

The management of this protocol will be aligned with country legislation and regulatory procedures.

Investigators will be cardiologists experienced in diagnosis of cardiomyopathies or physicians specialized in diagnosing patients with LVH. The sites involved (at least when performing feasibility) will be representative of their respective country in terms of practice. Participating physicians will not be influenced in their decision making and routine proceedings in any way.

The study will include approximately 1500 patients.

All assessments described in this protocol are performed as part of routine clinical practice or standard practice guidelines for the patient population and healthcare provider specialty in the countries where this non-interventional study is being conducted. Data, including individual study results, will be collected from these assessments, if performed.

## 9.2. Setting

### 9.2.1. Site Initiation

The cardiologists who agreed to participate in the study will receive a letter containing:

- A cover letter with a reply slip to be returned to Pfizer's logistics center;
- A study synopsis;
- The participating physicians' contracts, one copy of which should be returned to Pfizer's logistics center;
- A pre-paid envelope.

Once the contract has been signed and returned to Pfizer's logistics center, it will be validated by Pfizer.

A site initiation visit will be organized to present the protocol and its documentation.

This documentation will be sent by mail few days before initiation visit and it will be composed with:

- All study documents in the paper version (protocol, regulatory agreements, etc ...);

- Briefings and patient consent;
- Monitoring documentation (Screening and enrollment log, Subject identification code list, Site visit log, etc).

To initiate the site, Pfizer will have to receive some mandatory documents such as:

- Protocol Acceptance Form signed by the physician;
- The certificate of safety training;
- The signature sheet and delegations of duties log;
- The Curriculum Vitae of the physician and all the people involved in the project.

After reception of these documents, the physician and all the people involved in the study will receive the study website address and his/her own access code. They will find the following documents on the website:

- Regulatory authorities opinion;
- Ethics committee (EC) opinion;
- The study protocol and protocol amendment;
- The serious adverse events (SAE) declaration form.

In addition, data relating to the physician (year of registration, year of doctoral thesis, town where practicing etc.) can be uploaded to the website as well as the anonymized data regarding the patients.

Each physician investigator will be a single number (0001 to 00XX).

Each patient screened in the study will be assigned a number by order of inclusion in the study.

Therefore, each patient will be identified in the study by the center number and patient number (for example 0002-05 is the 5th patient included by the second site)

The physicians will be provided with a hotline number as well as an email address where they can ask questions about the conduct of the study.

### **9.2.2. Inclusion Criteria**

The study will enroll patients according to the eligibility criteria in participating countries. The recruiting centers will be representative of each country involved in terms of care management systems, of size and of practices (at least when performing feasibility).

To ensure equitable recruitment, each site will be limited to a 100 screened patient maximum.

All patients who met the inclusion and exclusion criteria will be invited to participate in the study.

An informed consent document, will be signed by each patient before any data collection (Appendix 1).

If a patient isn't included in the study for any reason, the non-inclusion register has to be completed (Appendix 2).

The enrollment visit will be performed at the time of inclusion, after the patients' acceptance of enrollment in the study and Informed Consent Document signature.

Data will come from medical records and will be collected in routine clinical practice. The enrollment visit will comprise a first section on patients' eligibility for every patient and a second section on the patient information, family history and clinical evaluation at the inclusion.

After the patient undergoes a Bone Scintigraphy and/or SPECT as part of standard of care (Annex 3) the images will be evaluated by the nuclear medicine specialist of the investigational center.

Scans will be defined at each site according to the internationally accepted grading:

*Grade 0 = absent cardiac uptake*

*Grade 1 = mild uptake less than bone*

*Grade 2 = moderate uptake equal to bone*

*Grade 3 = high uptake greater than bone*

For all patients with cardiac fixation at scintigraphy and/or SPECT the following data will be collected and incorporated in the CRF if available:

- Answers from questions regarding ATTR amyloidosis red flags
- Results from clinical laboratory tests and genotyping.

The patient will finish the study after this visit.

### **9.2.3. Centralized Review of Bone Scintigraphy (for all patients)**

In this study, all the scintigraphy/SPECT tests will be additionally reviewed by two external evaluators.

The objective of this evaluation will be to assess the level of discrepancy in the evaluation of the scintigraphy/SPECT images by different evaluators

All the scintigraphy/SPECT tests will be uploaded in a dedicated database via the study web site.

Two experts from the scientific committee members will connect to the study web site with personalized connection access. They'll review the scintigraphies/SPECT and enter their evaluation.

#### **9.2.4. Blood Samples Analyses**

Following the standard practice guidelines for the patient population with positive scintigraphy, blood and urine analyses are usually done to rule out AL amyloidosis. If performed, results of these tests will be collected.

Moreover, to differentiate between wild-type and variant ATTR-CM, genotyping are usually completed. If performed, results will be collected.

